1.6. Summary of Potential Risks and Benefits

KZR-616 is a selective and irreversible inhibitor of the immunoproteasome, a key intracellular function in immune effector cells. Selective inhibition of the immunoproteasome is

immunomodulatory rather than immunosuppressive in preclinical models. KZR-616 is demonstrated to have marked ability to block the inflammatory response in multiple mouse models of autoimmune disease, including but not limited to, models of RA, the progression of nephritis in 2 mouse models of SLE, and in the CIM mouse model of myositis.

KZR-616 is an investigational agent. To date, 2 studies in healthy volunteers using doses ranging from 7.5 to 75 mg KZR-616 weekly have been completed. In addition, a Phase 2 study in patients with SLE with or without LN (KZR-616-002) and a study of patients with PM or DM (KZR-616-003) are ongoing. Adverse events most often associated with KZR-616 to date have been ISRs that are transient, generally mild, and do not appear to increase in severity or frequency with repeat dosing. Tolerability of KZR-616 is improved with an initial 30 mg SC dose of KZR-616, followed by subsequent higher target doses of 45 or 60 mg. It is anticipated that participants in KZR-616-003E will have already demonstrated tolerability to KZR-616 following participation in KZR-616-003. Nonetheless, initial high doses of KZR-616 have been associated with at least one of the following signs/symptoms: hypotension, tachycardia, nausea, vomiting, dizziness, headache, pyrexia, rigors and/or chills.

Based on nonclinical studies with KZR-616, including a mouse model of myositis, the safety of KZR-616 at 45 mg in healthy volunteers, the safety of KZR-616 to date in 46 patients with SLE, and the potential benefit from anti-inflammatory activity induced by immunoproteasome inhibition, the overall positive benefit-risk balance of KZR-616 supports its continued development in patients with PM and DM.

For additional information, please refer to the current version of the KZR-616 Investigator's Brochure.

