9.5. Injection Site Reactions

In study participants who have received KZR-616 SC, ISRs, including bruising, discoloration, discomfort, erythema, induration, pain, pruritus and/or swelling, have been described in the majority of participants in KZR-616 studies to date; these events have been predominantly mild. No interventions have been formally studied to prevent or treat these reactions; however, local therapy such as topical antihistamines or corticosteroids may be helpful, and/or systemic antihistamines, anti-inflammatory drugs, and/or corticosteroids may be appropriate in more severe cases.

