10. STATISTICAL ANALYSES

This study is descriptive in nature, and no formal hypothesis testing will be performed. No formal statistical sample size estimation has been performed, since the number of patients in this study is determined by the number of patients who completed Study KZR-616-003 and enrolled in this study. Descriptive statistics, including the numbers and percentages for categorical variables; and the numbers, means, standard deviations (SD), medians, minimums and maximums for continuous variables will be provided by treatment group, by indication (DM, PM), and overall.

The number and percentage of patients who experience TEAEs, SAEs/death, AEs leading to treatment/study discontinuation, and treatment modification/delay due to AE(s) will be summarized by treatment group and overall. The number and percentage of patients experiencing any TEAE(s), overall, and by system organ class (SOC) and preferred term and by grade will be tabulated.

Continuous measures in laboratory, vital sign, ECG, and efficacy data will be summarized descriptively (mean, median, SD, and minimum and maximum values) by treatment group and overall and will be summarized by protocol-specified time point along with a summary of change from baseline at each time point. Changes in physical examinations will be listed for each patient and described. In addition, 95% confidence intervals may be provided to describe some continuous efficacy data.

Patient listings will be provided to support these summaries.

PK analyses will include determination of plasma levels of KZR-616 including C_{max} , T_{max} , and AUC.

Full Analysis Set (FAS): The FAS for summaries of efficacy endpoints will include all patients who receive KZR-616 in this study and have baseline and any post-baseline data. All observed data will be included in the statistical summaries. No missing data will be imputed except as pre-defined in the SAP.

Per Protocol (PP): A PP population may be used to analyze select efficacy endpoints, and will be based on KZR-616 exposure (time on treatment) and protocol deviations. The decision to summarize a PP population will be made prior to database lock.

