Safety Population: The safety population will include all patients enrolled who received at least one dose of KZR-616, and will be the population used for the analysis of safety. Adverse event data will be coded to system organ class and preferred term using Medical Dictionary for Regulatory Activities (MedDRA; Version 19.1 or later).

Data will be summarized for the following groups of patients based on the sequence of treatments received in Study KZR-616-003:

Group 1: Arm A (KZR-616:Placebo) from Study KZR-616-003 beginning on Day 1 (first dose of KZR-616) through the end of Study KZR-616-003E

Group 2: Arm B (Placebo:KZR-616) from Study KZR-616-003 beginning on Week 16 (first dose of KZR-616) through the end of Study KZR-616-003E

Groups 1 and 2 combined: from the first dose of KZR-616 in KZR-616-003 through the end of KZR-616-003E

Group 3: Arm B2: Patients receiving KZR-616 from Weeks 16-32 in KZR-616-003 followed by KZR-616 in OLE throughout KZR-616-003E, to evaluate patients who continuously received KZR-616 from KZR-616-003 through KZR-616-003E

Groups 1 and 2 are being assessed for any differences due to the intervening placebo treatment period in Group 1. The rationale for combining Group 1 and Group 2 is to encompass all KZR-616 treatment, and the rationale for assessing Group 3 is to encompass all continuous KZR-616 treatment.

Further details of the statistical methodology, including methods for handling missing data and early withdrawals, will be provided in an SAP that will be finalized prior to database lock. As KZR-616-003E is an open-label extension study, endpoints in addition to those described in [Section 2.2](#) may be conducted as described in the final SAP.

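### Section 10 specifies no adverse event summary by interval, per injection or for 003E alone, so its tables as written would not show whether injection site reactions persist or worsen in the extension

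*Combined protocol and SAP*

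**What the plan says.** The safety objective (Section 2.1) covers tolerability over the long term. On ISRs, Section 1.6 states: "Adverse events most often associated with KZR-616 to date have been ISRs". It adds that these reactions "do not appear to increase in severity or frequency with repeat dosing". Section 9.5 says that ISRs "have been described in the majority of participants in KZR-616 studies to date; these events have been predominantly mild". They are not among the adverse events of special interest named in Section 9.5.1.

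For adverse events, Section 10 tabulates "The number and percentage of patients experiencing any TEAE(s), overall, and by system organ class (SOC) and preferred term and by grade". It also counts patients with events leading to discontinuation or to treatment modification, and it plans patient listings. Continuous laboratory, vital sign, ECG and efficacy measures "will be summarized by protocol-specified time point along with a summary of change from baseline at each time point". No such sentence covers adverse events.

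Section 10 then defines the groups for summary. Group 1 is "Arm A (KZR-616:Placebo) from Study KZR-616-003 beginning on Day 1 (first dose of KZR-616) through the end of Study KZR-616-003E", a span that includes the placebo period. Group 2 starts at Week 16 of Study 003. The pooled set is "Groups 1 and 2 combined: from the first dose of KZR-616 in KZR-616-003 through the end of KZR-616-003E". Group 3 is the Arm B patients treated continuously from Study 003 into 003E. None of these begins at 003E Day 1. Further methodology is deferred to an SAP that is to be final before database lock.

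**The concern.** An ISR can recur with every injection. A count of patients affected at least once, over a window that opens with the first KZR-616 dose in Study 003, cannot change for a patient who already reacted there. That patient is a single yes whether the extension brings no further reactions or one every week.

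At stake is the tolerability objective for the commonest harm. Section 1.6 already makes a statement about repeat dosing, and up to 96 further weekly injections are the natural evidence on it. As written, the tables would give one cumulative figure per term and grade, with nothing to show when the reactions occurred.

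**Working it through.** The plan gives no ISR rate and no sample size calculation, so there is no figure to reproduce. The question is how far the cumulative count moves under different courses.

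**Inputs**
- Patients: 24, the maximum in Section 4.1.
- Study 003 doses of KZR-616: 16. This is an assumption, from Weeks 16-32 in Section 10 and weekly dosing.
- 003E doses: n = 48 or 96 (Section 3.1).
- Assumed: s, the share of patients susceptible to ISRs; p, their per-injection probability in Study 003; f, the multiplier on p in 003E (0.1 fading, 1 stable, 1.5 or 2 worsening).

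**Formula.** Patients ever affected = 24 × s × [1 − (1 − p)^16 × (1 − f·p)^n].

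**Worked case, s = 1, p = 0.05, n = 48.** 0.95^16 = 0.440.
- Fading: 0.995^48 = 0.786, so 24 × (1 − 0.440 × 0.786) = 15.7.
- Stable: 0.95^48 = 0.0853, so 24 × (1 − 0.0375) = 23.1.
- Doubled: 0.90^48 = 0.0064, so 24 × (1 − 0.0028) = 23.9.

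**Range** (differences taken before rounding)

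| s | p | n | Fading (f = 0.1) | Stable | Doubled (f = 2) | Stable − fading | Doubled − stable |
|---|---|---|---|---|---|---|---|
| 1.0 | 0.05 | 48 | 15.70 | 23.10 | 23.93 | 7.40 | 0.83 |
| 0.8 | 0.05 | 48 | 12.56 | 18.48 | 19.15 | 5.92 | 0.67 |
| 0.8 | 0.05 | 96 | 13.98 | 19.14 | 19.20 | 5.16 | 0.06 |
| 0.8 | 0.10 | 48 | 17.00 | 19.18 | 19.20 | 2.17 | 0.02 |
| 0.8 | 0.20 | 48 | 19.00 | 19.20 | 19.20 | 0.20 | 0.00 |
| 0.8 | 0.20 | 96 | 19.12 | 19.20 | 19.20 | 0.08 | 0.00 |

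**Unequal risk.** Let each patient's rate follow a Beta(0.4, 1.6) distribution (mean 20%), with f·p capped at 1 and n = 48. Then 64% are affected before 003E (24 × 0.642 = 15.4). The final count is 16.2 if rates fall by 90%, 19.0 if unchanged, 19.6 if they rise by half and about 20.0 if they double. Fading moves it by 2.8 patients and worsening by 0.6 to 1.0.

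**Lower rates.** At p = 0.04, s = 1, n = 48, stable gives 24 × (1 − 0.96^64) = 22.24 and doubled gives 24 × (1 − 0.96^16 × 0.92^48) = 23.77, a difference of 1.5. The masking of worsening weakens as the rate falls.

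**Share of the final figure already set by dose 16**, at a constant rate with n = 96: [1 − (1 − p)^16] / [1 − (1 − p)^112] = 56%, 82% and 97% at p = 0.05, 0.10 and 0.20. If all patients are susceptible and 51% are affected by dose 16, the share is 51% (n = 96) to 54% (n = 48).

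**What other summaries would show** (s = 0.8; fading / stable / doubled)

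| p | Ever affected in 003E alone, n = 48 | Affected in a 12-week interval: 24·s·[1 − (1 − f·p)^12] | ISRs per 100 injections: 100·s·f·p |
|---|---|---|---|
| 0.05 | 4.1 / 17.6 / 19.1 | 1.1 / 8.8 / 13.8 | 0.4 / 4 / 8 |
| 0.20 | 11.9 / 19.2 / 19.2 | 4.1 / 17.9 / 19.2 | 1.6 / 16 / 32 |

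Separating 003E from Study 003 would reveal fading, but at the higher rate it would still hide worsening. The 12-week count helps further, and the per-injection rate separates all three courses at both rates.

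**The case against.** The best reply is that the plan holds more than a yes/no count and that Section 10 is not the last word. Events are tabulated by grade, and patient listings are planned. A change of grade is recorded as a separate event (Section 9.1.2), and dates are collected (Section 9.1.6). With at most 24 patients, a dated listing can be read. The sentence on groups is general, and treatment-emergent is not defined for 003E. Section 2.2.1 mentions Study 003 data only for efficacy endpoints, and adverse events are collected from consent (Section 9.1.5). A 003E-only table is therefore neither specified nor excluded, and the SAP may add one. ISRs have been mostly mild, and the study is descriptive.

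Much of this stands, and it rules out several stronger readings:
- A reader might infer that ISRs are recorded only as ever or never. The grade tables and listings contradict that.
- A reader might infer that the study could neither support nor refute the Section 1.6 statement. Dated records could be used for that; what is missing is a planned summary.
- A reader might infer that the final figure is certain to be mostly fixed before 003E, or that fading, stable and worsening courses all look alike. Both depend on rates that the documents do not give, and at 5% fading shows clearly.
- A reader might infer that ISRs will be scattered over many preferred terms with no single figure. The instruction to record each sign separately (Section 9.5.1.1) concerns the systemic tolerability complex; Section 9.5 does not say how ISRs are entered or coded.

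The reply does not supply timing. Grade over the whole window has none, a listing leaves the summarizing to the reader, and the groups as written all include Study 003 treatment.

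**Conclusion.** The point holds as a cheap improvement to the safety summaries. Followed as written, Section 10 would not show whether ISRs persist or worsen in the extension.

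At assumed rates of 5% per injection or more, stable and worsening reactions differ by about one patient in 24 or fewer in the cumulative count, and by almost none at 10% or more when risk is similar across susceptible patients. At 4% the gap can reach 1.5 patients. Fading is visible at low rates (about 5 to 7 of 24 at 5%, with 80% to 100% of patients susceptible). It is not visible at 20% if risk is similar across patients, and it is partly visible (about 3 of 24) if risk varies widely.

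These sizes rest on assumed rates, on 16 Study 003 doses and on independent reactions within a patient. That the tables carry no timing rests on the text of Section 10 alone, read without the SAP to which it defers.

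**What to change.** In Section 10 and the SAP, keep the existing tables and add one for a pooled, predefined group of injection-site preferred terms, with 003E shown separately from the Study 003 KZR-616 period.

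- For each 12-week 003E interval, give the number dosed, patients with at least one reaction, reactions per 100 injections given, and maximum grade.
- Give the Study 003 KZR-616 period its own column. It lasts 16 weeks, so compare it with the 003E intervals by the per-injection rate and not by the percentage ever affected.
- Count a grade change within one continuing reaction as one reaction, because Section 9.1.2 would otherwise inflate the numerator.

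Onset dates come from the adverse event records (Section 9.1.6), and injections given come from the dosing records, including the diary for home doses (Section 5.4).

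The cost is one SAP paragraph and one table. Intervals after Week 48 will hold fewer patients, because dosing stops for everyone once the last patient enrolled reaches 48 weeks, so the number dosed must stand beside each figure. The per-injection rate is sound only if recurrent reactions are entered as separate records. Section 9.1.6 asks for the date of first occurrence, and the diary records doses, not reactions. Where recurrences are not entered separately, rely on patients affected per interval. No change to dosing or clinical management is involved.

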Subcutaneous administration of KZR-616 resulted in consistent, dose-proportional PK. At all dose levels tested, KZR-616 was rapidly absorbed and cleared with no accumulation following weekly repeat doses. Drug levels were below the limit of quantitation by 24 hours post dose. The pharmacology was consistent across subjects, with low inter-subject variability in both exposure and target inhibition, regardless of concomitant treatment with or without corticosteroids and antihistamines. Though KZR-616 is a weak time-dependent inhibitor of Cytochrome P450 (CYP) 3A4 and a substrate of P-glycoprotein (P-gp), the rapid clearance and extrahepatic metabolism of KZR-616 by epoxide hydrolases strongly suggest that there is minimal risk for a DDI.

Across a dose range from 7.5 to 75 mg, SC administration of KZR-616 resulted in selective and dose-dependent inhibition of peripheral blood mononuclear cell (PBMC) CT-L activity (predominantly immunoproteasome), with doses of ≥ 30 mg resulting in mean inhibition of PBMC CT-L activity $>80\%$ and mean inhibition of whole blood CT-L activity (predominantly constitutive proteasome) $\leq 36\%$. Data further showed that despite incomplete recovery of immunoproteasome activity on Day 7 (6 days after dosing), there was not an accumulation of proteasome inhibition. From a PK and pharmacodynamic (PD) perspective, weekly SC administration of KZR-616 appeared equivalent to serial episodic dosing.

1.4. Rationale for Use of KZR-616 in the Proposed Study Populations, and Rationale for the Study

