6.1.2. Suggested Measures to Improve KZR-616 Tolerance

Initial SC doses of 60 mg KZR-616 are associated with at least one of the following signs/symptoms: hypotension, tachycardia, nausea, vomiting, dizziness, headache, pyrexia, rigors and/or chills. These signs/symptoms typically begin within 8 to 24 hours after dosing, and usually resolve within 48 hours after dosing.

Although the numbers are small, the percentage of patient reporting treatment-emergent AEs (TEAEs) of the above signs/symptoms appears to be lower in patients who received KZR-616 as step-up doses and/or with pre-/post-dose prophylaxis, suggesting that these methods are effective at tolerizing patients to higher doses of KZR-616.

Step-up Dosing

It is unknown whether patients who start, stop, and then resume treatment with KZR-616 will experience tolerability issues (eg, patients randomized to Arm A of Study KZR-616-003). Thus, to maintain the blind for Study KZR-616-003, all patients enrolling in Study KZR-616-003E will receive an initial dose of 30 mg KZR-616, to be followed weekly by the target dose of 45 mg.

Pre/Post Dose Prophylaxis

Prophylactic measures may be considered if any of the signs and/or symptoms listed above develop, and may be used as treatment, either while the patient is at the study site or after leaving the study site. Measures that have been demonstrated to reduce the incidence and severity of infusion-related reactions with other proteasome inhibitors include the following:

- Fluid hydration, eg, 250-500 mL oral (or intravenous [IV] if necessary) of an electrolyte solution up to 48 hours prior to dosing, or up to 24 hours after dosing if symptoms are present

- Antiemetics, non-sedating antihistamines, and/or acetaminophen (if fever is present)

If additional guidance for improving initial tolerability symptoms is required, the Medical Monitor should be consulted. Home health providers do not provide or administer any of the fluids or medications listed above.

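### Section 10's pooled window, described as all KZR-616 treatment, also spans Arm A's 16 placebo weeks and any inter-study gap, and no rule in the supplied document separates adverse events by period of onset

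*Combined protocol and SAP*

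**What the plan says.** Section 10 of the protocol summarizes data by the treatment sequence received in Study 003. Group 1 is Arm A (KZR-616 then placebo) from Day 1 of Study 003 to the end of 003E. Group 2 is Arm B (placebo then KZR-616) from Week 16 of Study 003 to the end of 003E. The pooled group is "Groups 1 and 2 combined: from the first dose of KZR-616 in KZR-616-003 through the end of KZR-616-003E". Its purpose is given as follows: "The rationale for combining Group 1 and Group 2 is to encompass all KZR-616 treatment".

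The section knows that Group 1 contains placebo time: "Groups 1 and 2 are being assessed for any differences due to the intervening placebo treatment period in Group 1". It does not say that this time is removed from any total.

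The planned safety statistic is a patient count: "The number and percentage of patients who experience TEAEs, SAEs/death, AEs leading to treatment/study discontinuation", together with treatment modifications or delays, by treatment group and overall. Treatment-emergent adverse event is spelled out in the List of Abbreviations but is given no time window. Other methods are deferred: "Further details of the statistical methodology, including methods for handling missing data and early withdrawals, will be provided in an SAP". No separate SAP text is in the supplied document.

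Section 6.1 allows the first open-label dose up to 8 weeks after the Week 32 Visit of Study 003.

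**The concern.** The pooled group is described as KZR-616 treatment, yet its boundaries take in weeks when Arm A patients were on placebo and, in either arm, weeks between the two studies when no drug is scheduled. Section 6.1.2 itself treats Arm A as interrupted treatment: "It is unknown whether patients who start, stop, and then resume treatment with KZR-616 will experience tolerability issues".

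Each patient counts once per row over a fixed denominator. Adding off-drug weeks to the window can therefore only hold or raise the percentage shown. In a study of at most 24 patients, one added patient is visible in a preferred-term row. Long-term safety is one of the two stated objectives and the study is purely descriptive, so these tables are the product. At stake is a pooled safety table whose label does not match its contents.

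**Working it through.** **Plan's own figure.** Maximum participation in 003E is 96 weeks of dosing + 12 weeks of follow-up = 108 weeks, as Section 3.1 states. Table 1 agrees: (108 − 1) × 7 + 1 = Day 750.

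**Off-drug time inside the window.**
- Arm A placebo: Week 32 (Section 3.1) − Week 16 (Section 10) = 16 weeks = 112 days.
- Inter-study gap: 0 to 8 weeks (Section 6.1).
- Open-label dosing: 48 weeks (planned course of the last patient enrolled) to 96 weeks (Section 3.1).
- Group 1 window = 32 + gap + dosing + 12. Off-drug share before the last dose = (16 + gap) / window.

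| Open-label dosing | Gap | Group 1 | Pooled, 12:12 split assumed |
|---|---|---|---|
| 96 wk | 0 | 16/140 = 11.4% | 192/3168 = 6.1% |
| 96 wk | 8 wk | 24/148 = 16.2% | 384/3360 = 11.4% |
| 48 wk | 0 | 16/92 = 17.4% | 192/2016 = 9.5% |
| 48 wk | 8 wk | 24/100 = 24.0% | 384/2208 = 17.4% |

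Pooled figures are patient-weeks for 24 patients who all complete: 12 × Group 1 window + 12 × (Group 1 window − 16). The arm split is not in the documents.

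**Does another rule remove this time?** Sections 9.1.5 and 9.2.2 set collection and reporting limits for 003E. They do not sort Study 003 events into drug or placebo. Section 1.5 promises consideration of treatment periods but refers back to Section 10. Section 2.2.1 allows efficacy endpoints to use Study 003 treatment periods; Section 2.2.2 has no matching sentence for safety.

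**One patient.** An Arm A patient whose only event of a kind began on placebo adds 1/24 = 4.2 points to the pooled row (1/18 = 5.6 if only 18 enrol). In Group 1 that patient adds 1/12 = 8.3 points at 12:12 (1/8 = 12.5 to 1/16 = 6.3 for 8 to 16 Arm A patients).

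**Expected size, as an illustration.** The documents give no event rates. Assume a 12:12 split, no gap, and a constant-rate background event affecting a proportion p of patients over K weeks on KZR-616, where K = 16 + 48 = 64 to 16 + 96 = 112. A patient enters the row only because of placebo if there is no event in the K weeks or the 12-week follow-up and at least one in the 16 placebo weeks:

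q = (1 − p)^((K + 12)/K) × [1 − (1 − p)^(16/K)]

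| p | K | q | Expected patients, 12q | Pooled points, 100 × 12q/24 | At least one, 1 − (1 − q)^12 |
|---|---|---|---|---|---|
| 10% | 112 | 0.0133 | 0.16 | 0.7 | 15% |
| 10% | 64 | 0.0229 | 0.28 | 1.1 | 24% |
| 30% | 112 | 0.0335 | 0.40 | 1.7 | 33% |
| 30% | 64 | 0.0559 | 0.67 | 2.8 | 50% |

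**Crediting early placebo days to drug.** With an illustrative 30-day residual window, 112 − 30 = 82 days (11.7 weeks) remain off drug. Replacing 16 by 11.7 and K + 12 by K + 12 + 30/7 gives q = 0.0097 to 0.0404 at the two extremes. That is 0.5 to 2.0 points, with a chance of 11% to 39%. With a 12-week window, 112 − 84 = 28 days remain.

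**The case against.** Several points on the other side stand.

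- **The SAP may settle it.** A reader might infer that the deferral covers only missing data and early withdrawals. It does not: those are introduced as examples, and a treatment-emergent definition is ordinary SAP content. What is shown is that Section 10 states an unbroken window and that nothing supplied qualifies it. It is not shown that the final analysis will be wrong.
- **Section 10 speaks of data, not safety.** It does not say outright that treatment group in the adverse-event paragraph means these groups. They are, however, the only groups it defines.
- **Disclosure.** A reader might infer that nobody could tell which events arose on drug. That goes too far. The placebo period is named, Group 2 contains no placebo weeks, Groups 1 and 2 are reported separately, and listings are promised. None of this changes the pooled or Group 1 counts.
- **Residual effect.** It is tempting to treat every placebo week as cleanly off drug because Section 1.3 says "Drug levels were below the limit of quantitation by 24 hours post dose". The same section reports incomplete recovery of immunoproteasome activity on Day 7, Section 1.6 calls the inhibition irreversible, and Section 7.2.8 cites full recovery within 3 days. The documents do not settle how long an effect persists, so some placebo days may fairly belong to drug.
- **Direction.** Any error over-counts KZR-616 events, which is the cautious side for safety. The table would still not show what its label says.

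**Conclusion.** The point holds on the text and should be fixed. Followed literally, Section 10 presents Arm A's placebo weeks, and any gap in which events are collected, as KZR-616 experience in the pooled group. Group 1's own total mixes the same periods.

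The size is modest. The 4.2 points per affected patient is arithmetic on the maximum enrolment. The 0.7 to 2.8 points per term (0.2 to 0.7 of a patient) rests on the assumed 12:12 split, a constant 10% to 30% background event and no gap. No gap effect is estimated, because capture of those events depends on when 003E consent is signed and on Study 003 rules that are not supplied.

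No hypothesis test, power or error rate is involved. The documents do not support extending the point to visit-based measures in general: continuous data "will be summarized by protocol-specified time point along with a summary of change from baseline at each time point", and at 003E treatment visits both arms are on open-label drug.

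**What to change.** In Section 10 and the SAP, define a treatment-emergent event and assign each adverse event in the pooled summary to its period of onset:

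1. KZR-616 course: first to last dose of the course plus a residual window that the sponsor fixes in advance, with a second window as a sensitivity analysis.
2. Arm A placebo period beyond that window.
3. Inter-study gap.
4. Post-treatment follow-up after the final dose.

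Keep events up to the EOS Visit either in the KZR-616 column or in their own labelled column. If a 30-day cut were applied to every course with no such column, events on days 31 to 84 of the 12-week follow-up would have no place in the table, although Section 9.1.5 collects them. Show the placebo and gap columns beside the KZR-616 column, and keep Groups 1 and 2 as separate sequence summaries.

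The cost is modest programming before database lock, using Study 003 arm and dose dates once that study is unblinded. No new data are collected. The drawbacks are smaller period-specific columns and some dependence on the residual window. The pooled KZR-616 percentages can only stay the same or fall, which is why the other columns must stand next to them.
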